6.2.2. Duration of Response

Analysis of treatment effect based on Duration of Response (defined in [Section 3.2.2](#)) will be conducted on participants from the Safety Set with a BOR of CR or PR and will include all data collected from the time of tumor response until disease progression, death or initiation of a new anticancer therapy, whichever occurs first, regardless of tolerability or duration on treatment.

DoR will be calculated as follows:

DoR (months) = [first date of PD or death/censoring – first date of CR/PR subsequently confirmed+1]/30.4375.

DoR data will be censored as follows:

- For participants who start a new anticancer therapy prior to an event (PD or death), censoring will be at the last adequate tumor assessment (see [Section 5.2.7](#)) prior to the start of new anticancer therapy. Note: if date of progression occurs on the same date as the start of new anticancer therapy, the progression will be counted as an event.
- For participants with documented progression or death after two or more missing tumor assessments, censoring will occur at the last adequate tumor assessment prior to the missing assessments. In this study antitumor activity will be assessed through radiological tumor assessments conducted at screening and every 12 weeks until disease progression regardless of initiation of subsequent anticancer therapy. The allowable time window for disease assessments is ± 1 week while on treatment. Therefore time without adequate assessment is defined as 24 weeks plus 2 weeks.
- All other participants alive without objective progression will be censored on the date of the last adequate tumor assessment.

The date of tumor response at each nominal timepoint based on the investigator assessments will be used for determining the dates of last adequate assessment for censoring purposes.

The censoring and event date options to be considered for the DoR analysis are presented in Table 2.

Table 2. Outcome and Event Dates for DoR Analyses

Scenario	Date of event/censoring	Outcome
Progression or death ≤ 26 weeks after last adequate tumor assessment	Date of progression or death	Event
Progression or death > 26 weeks after the last adequate tumor assessment	Date of last adequate assessment documenting no PD prior to new anticancer therapy or missed assessments	Censored
No progression		
New anticancer therapy given prior to PD		

Kaplan-Meier estimates (product-limit estimates) will be presented together with a summary of associated statistics including the median DoR time with two-sided 95% CIs. The CIs for the median will be calculated according to Brookmeyer and Crowley. When the number of participants with PD after a confirmed CR or PR is small, the use of Kaplan-Meier method is limited due to high number of censored observation, so the DoR will be summarized using number (%) of participants with events and of participants censored with DoR in the following categories: less than 6 months, $\geq 6 - < 9$, $\geq 9 - < 12$, $\geq 12 - < 15$, $\geq 15 - < 18$, $\geq 18 - < 21$, $\geq 21 - < 24$, and ≥ 24 months.

Frequency (number and percentage) of participants with each event type (PD or death) and censoring reasons will be presented along with the overall event and censor rates.

Reasons for censoring will be summarized according to the categories in Table 3. If a participant meets multiple definitions for censoring the list will be used to define the hierarchy.

Table 3. Censoring Reasons and Hierarchy for DoR Analyses

Hierarchy	Condition	Censoring Reason
1	Start of new anticancer therapy before event.	Start of new anticancer therapy
2	Event more than 26 weeks from last adequate post-baseline tumor assessment	Event after missing assessments ^a
3	No event and [withdrawal of consent date \geq first date of CR/PR or End of study (EOS) = Subject refused further follow-up]	Withdrawal of consent
4	No event and lost to follow-up in any disposition page	Lost to follow-up
5	No event and none of the conditions in the prior hierarchy are met	Ongoing without an event

^a more than 26 weeks after last adequate tumor assessment.

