9.4.2. Analysis of Secondary Endpoints

Secondary endpoints are confirmed ORR and DoR as assessed by the investigator using RECIST version 1.1.

ORR: ORR is defined as the percent of participants with best overall response as confirmed CR or confirmed PR according to RECIST version 1.1. ORR will be provided along with the corresponding 95% CI based on Wilson's Score Method.

DoR: DoR is defined as the time from the first documentation of objective tumor response (CR or PR) to the first documentation of disease progression or death due to any cause, whichever occurs first. For participants whose responses proceed from PR to CR, the onset of PR is taken as the onset of response. DoR will be summarized in the population of participants with a confirmed CR or confirmed PR using the Kaplan Meier method and will be displayed graphically where appropriate. The median event time (if appropriate) and 2-sided 95% CI for the median will be provided. Censoring for DoR will be described in the SAP. In case the number of participants with Progressive Disease after a confirmed CR or confirmed PR is small, the use of Kaplan Meier method may be limited, and descriptive statistics may be provided.

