- Population-level summary: Kaplan-Meier Median of DoR and 2-sided 95% CI.

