3.2.2. Duration of Response

DoR based on investigator assessment is defined, for participants with a confirmed objective response, as the time from first documentation of objective response (CR or PR per RECIST v1.1, whichever is earlier) to the date of first documentation of PD or death due to any cause, whichever occurs first. The censoring rules for DoR are presented in [Section 6.2.2](#).

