5. GENERAL METHODOLOGY AND CONVENTIONS

All analyses will be performed at study participant data set release at the end of study, defined as 1 year after the last participant first visit (LPFV) date in the study.

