5.2.11. Analyses for Time-to-Event Endpoints

Time to event endpoint will be summarized using the Kaplan-Meier method and estimated survival curves will be displayed graphically if appropriate. The median event time (if appropriate) and 2-sided 95% CI for the median will be provided based on the Brookmeyer-Crowley method. In case the number of participants with PD after a confirmed CR or confirmed PR is small for the Kaplan-Meier method, descriptive statistics will be provided.

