5.3. Methods to Manage Missing Data

Unless otherwise specified, all data will be evaluated as observed, and no imputation method for missing values will be used.

Any imputations will occur at the analysis dataset level. Additionally, in all data listings imputed values will be presented and flagged as imputed.

Missing statistics, eg, when they cannot be calculated, should be presented as 'ND' for not done, 'NR' for not reached or 'NA' for not applicable. For example, if N=1, the measure of variability cannot be computed and should be presented as 'ND' or 'NA'.

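### The SAP drops Kaplan-Meier for duration of response when progressions are few; that is no reason to drop it, and it should always be shown, with the duration bands as a supplement

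*SAP*

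**What the plan says.** The DoR estimand in SAP 2.1.2 ends with "Population-level summary: Kaplan-Meier Median of DoR and 2-sided 95% CI", with no exception for sparse data. SAP 6.2.2 likewise opens by promising Kaplan-Meier estimates and a median with a Brookmeyer-Crowley interval.

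The same paragraph then provides for the case in which the number of responders with progressive disease (PD) is small: "the use of Kaplan-Meier method is limited due to high number of censored observation, so the DoR will be summarized using number" and percentage of participants with events and censored, in eight bands from under 6 months to 24 months or more. SAP 5.2.11 has the same rule: when that number "is small for the Kaplan-Meier method, descriptive statistics will be provided". Protocol 9.4.2 is softer: "the use of Kaplan Meier method may be limited, and descriptive statistics may be provided". None of the three says how few is small, and none says that Kaplan-Meier is kept beside the bands.

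Four other provisions bear on this:

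- SAP 3.2.2 ends DoR at the "first documentation of PD or death due to any cause, whichever occurs first", so death is an event as well as PD.
- SAP 5.3 already has codes for statistics that cannot be computed, including "NR' for not reached or 'NA' for not applicable".
- SAP 6.2.2, on censoring: "All other participants alive without objective progression will be censored on the date of the last adequate tumor assessment".
- SAP 5 sets the analysis at end of study, "defined as 1 year after the last participant first visit (LPFV) date in the study". Follow-up is therefore shortest for those who enrol last.

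**The concern.** The stated ground is wrong. Kaplan-Meier exists to handle censored durations. Few events can leave the median not estimable, which the NR code already covers, but they do not invalidate the curve or the probability of still being in response at 6, 9 or 12 months while participants remain at risk. The substitute provides neither the estimand's summary nor any other estimate that allows for censoring and carries a confidence interval.

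The trigger is also loose. It has no number, so it would be judged with the data in hand in an open-label study. It counts PD only, although deaths are DoR events too.

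Finally, the band in which an ongoing responder falls is set partly by enrolment date. The table does separate events from censored participants, so it misleads only if the band percentages are read as durability rates. Under the fallback, however, the study report would offer nothing better to read.

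**Working it through.** The documents give no precision figure for DoR and no number for the trigger, so there is no planned figure to reproduce. The check has two parts: arithmetic from the documents' own schedule, and simulation under stated assumptions.

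**1. How follow-up limits the bands**

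Inputs: end of study 1 year after last participant first visit (LPFV; SAP 5, Protocol 13.1); screening up to 28 days (Protocol 6.1); scans every 12 weeks ±1 week (Protocol 7.1.1); ongoing responders censored at the last adequate scan; DoR in months = (days + 1)/30.4375 (SAP 6.2.2).

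- Last enrollee, first dose to end of study: 365 − 28 = 337 days to 365 − 0 = 365 days. Scans at weeks 12, 24, 36 and 48 (day 336) fit; week 60 (day 420) does not.
- Response first seen at week 12, ongoing at week 48: (252 + 1)/30.4375 = 8.3 months. At the edges of the windows, week 11 to week 49: (266 + 1)/30.4375 = 8.8 months. On scheduled scans this participant cannot enter any band of 9 months or more, however durable the response.
- To be counted at 12 months or more, a week-12 responder needs five further 12-week intervals, since four give only (336 + 1)/30.4375 = 11.1 months. Five give (420 + 1)/30.4375 = 13.8 months, at week 72 (day 504). The first dose must then fall at least 504 − 365 = 139 days (4.6 months) before LPFV, or 132 days if that scan is done a week early.

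**2. Does Kaplan-Meier fail when events are few?**

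Assumptions, none from the documents: 65 responders, all first seen at week 12; exponential DoR; 14 days of screening; uniform accrual over 6, 12 or 18 months; PD dated at the next 84-day scan; no dropout. The last scan grid point before 12 months is day 336, so the true 12-month value is 0.5^(336/30.4375/median). This gives 59.4%, 80.9% and 85.3% for medians of 14.7, 36 and 48 months. The 14.7 is the pivotal trial's median PFS, used only as a stand-in.

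| Assumed median DoR | Mean events | True 12-month value | Kaplan-Meier mean | Crude share in bands ≥12 months |
|---|---|---|---|---|
| 14.7 months | 25 / 30 / 34 (accrual 6 / 12 / 18 months) | 59% | about 59% | 9% / 34% / 42% |
| 36 to 48 months | 9 to 17 | 81% to 85% | 81% to 86% | 12% to 61% |

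In the second row the 95% CI (log-log, Greenwood variance) covered the truth in 95% to 96% of trials and was 18 to 21 points wide. With 30 responders, a median of 14.7 months and accrual over 6 or 12 months (mean 12 to 14 events), coverage was 95% and width 35 to 37 points.

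The crude share at 14.7 months changes to 23% / 41% / 47% if an extra scan is done at study close under the 6-week rule in Protocol 7.1.1, and to 8% / 28% / 35% with 15% yearly dropout.

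**3. A second set of assumptions**

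A separate simulation used a 70% response rate among 100 treated, medians of 9 to 48 months, accrual over 6 to 24 months, and dropout of 0 or 2% per month. Its 24 scenarios had about 9 to 53 events and 25% to 87% censoring. Mean Kaplan-Meier estimates at 6, 9 and 12 months were always within 0.6 points of the truth. The crude share at 12 months or more fell short by 8 to 70 points. As one sparse example (median 48 months, 12-month accrual, 2% monthly dropout; 11 events in 70 responders, 84% censored), the truth was 85.3%, Kaplan-Meier 85.1% (SE 4.6 points) and the crude share 40.3%. The median was not reached in 98% of runs.

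**The case against.** Five points can be made for the plan.

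- **The text is ambiguous.** SAP 6.2.2 says without condition that Kaplan-Meier estimates will be presented, then calls the method limited, not omitted. This is partly right, but the rule goes on to say what DoR will be summarized with instead, and nothing keeps both. At the least it needs a clarifying sentence.
- **Little is lost.** The estimand asks only for the median, which would usually be NR in the sparse scenarios; fixed-time probabilities are planned nowhere. True, and for that reason they should be added: with an unreached median they carry the information.
- **The rule may never apply.** With a 14.7-month median the simulations give 25 to 34 events on average, and fewer than 10 in at most 0.1% of trials. The sparse scenarios need a median of 36 to 48 months, well above the only benchmark in the documents. This stands and limits the severity.
- **Kaplan-Meier can be of little use with very few responders.** With 10 to 15 responders and 3 to 6 events, the 12-month interval is 46 to 58 points wide and is undefined in up to 5% of trials. That is imprecision, not bias; numbers at risk and the interval show it openly. Kaplan-Meier also assumes non-informative censoring, which censoring at new anticancer therapy may strain, but the bands do not cure that.
- **The crude share is not an estimator the SAP proposes.** Correct: events and censored participants are listed separately. The gaps above measure the cost of a misreading.

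The move from may in the protocol to will in the SAP is not itself a fault, because both documents let the SAP modify the protocol. It does make the substitution firmer.

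**Conclusion.** The concern holds. Followed as written, the rule removes the only censoring-adjusted DoR estimate on a ground that is not valid, departs from the SAP's own estimand, and does so on an unquantified trigger. In every scenario examined Kaplan-Meier stayed essentially unbiased, while the crude share at 12 months or more fell below the truth, by 8 to 70 points across the 24 scenarios of the second simulation. The size of that gap rests on assumed response rate, accrual, DoR distribution, scan timing and dropout. The 8.3-month ceiling for the last enrollee follows from the documents' schedule for a response first seen at week 12. The importance is moderate: DoR is a descriptive secondary endpoint in a single-arm safety study without hypothesis tests, so what is at risk is the clarity of the report, not a decision. It should be corrected before the analysis.

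**What to change.** In SAP 5.2.11 and 6.2.2, delete the sentences that let descriptive counts stand in for Kaplan-Meier. Whatever the number of events, present:

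- the Kaplan-Meier curve with numbers at risk;
- the median, or NR, with its Brookmeyer-Crowley 95% CI;
- Kaplan-Meier probabilities of continued response at 6, 9 and 12 months with 95% CIs, shown as NA where not estimable.

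Keep the banded table of events and censored participants as a supplement, with a footnote that its percentages do not estimate durability of response. No definition of small is then needed. Align Protocol 9.4.2 at the next amendment.

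The cost is SAP wording and a little standard output from the same data. With few participants at risk the intervals will be wide, and the report should show that.

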6.3. Other Endpoint(s)

Not applicable.

6.4. Subset Analyses

Not applicable.

6.5. Baseline and Other Summaries and Analyses

6.5.1. Baseline Summaries

6.5.1.1. Demographic Characteristics

The following demographic and baseline characteristics will be summarized by number and percentage:

- Gender (male, female);
- Age (18-<45; 45- <65; \geq 65);
- Eastern Cooperative Oncology Group (ECOG) Performance status.

Age (continuous) and weight (kg) will be summarized with descriptive statistics (mean, median, Std Dev, minimum, and maximum).

6.5.1.2. Medical History

Medical history will be coded using the most current version of MedDRA and summarized by MedDRA's SOC and PT from the 'Medical History' CRF page. Each participant will be counted only once within each PT or SOC. Summaries will be ordered by primary SOC and PT in descending order of frequency. Separate summaries will be provided for past and present conditions.

6.5.1.3. Disease Characteristics

The following baseline disease characteristics will be summarized by number and percentage:

- Measurable disease at baseline (yes/no);
- Involved tumor sites at baseline;
- Number of sites of disease at baseline (1, 2, ≥ 3).

Involved tumor sites at baseline will be derived from target and non target lesions at baseline. Each participant will be counted once per organ. Similarly, number of sites of disease at baseline will be derived by counting the number of unique organ sites from target and non target lesions at baseline. "Other" will be counted as one organ site.

6.5.1.4. Prior Anticancer Therapy

The prior anticancer therapies are collected under the 'Response to Regimen', 'Prior Radiation Therapy' and 'Non-drug Treatments' (with 'Category' = 'Prior Cancer Surgery') CRF pages.

The number and percentage of participants in each of the following anticancer therapy categories will be tabulated:

- Participants with at least one type of prior anticancer treatment;
- Participants with at least one prior anticancer drug therapy;
- Participants with at least one prior anticancer radiotherapy;
- Participants with at least one prior anticancer surgery.

Prior anticancer drug therapy will be summarized as follows based on the number and percentage of participants:

- Number of prior anticancer therapy regimens: missing /1/2/3/ ≥ 4 ;
- Type of prior anticancer therapy;

- Intent of Therapy: Neo-Adjuvant / Adjuvant / Advanced – Metastatic.

The prior anticancer drugs will be coded in the World Health Organization (WHO) Drug coding dictionary.

6.5.2. Study Conduct and Participant Disposition

6.5.2.1. Disposition

A summary of the number of participants enrolled by site will be provided for the Enrolled Set.

Discontinuations from study (overall and by main reason for study discontinuation) will be summarized using the Enrolled Set. Discontinuations from study treatment (overall and by main reason for study treatment discontinuation) will be summarized using the Safety Set.

Discontinuations from study treatment due to adverse events will be identified as either related or not related to study treatment. If causality is missing, the event will be considered related to treatment. If multiple events lead to study treatment discontinuation and at least one was considered related, discontinuation will be reported as related to study treatment.

6.5.2.2. Protocol Deviations

Protocol deviations will be compiled prior to database closure and will be summarized by category (n(%)) for the Enrolled Set. Categories will be assigned by the study Clinician.

6.5.3. Study Treatment Exposure

Exposure will be summarized for the Safety Set.

6.5.3.1. Exposure to dacomitinib

The summary of treatment exposure for dacomitinib will include the following information:

- Treatment duration (weeks);
- Cumulative dose (mg);
- Dose intensity (mg/week);
- Relative dose intensity (%).

The duration of dacomitinib (in weeks) is defined as:

$$\text{Treatment duration (weeks)} = (\text{last dose date} - \text{first dose date} + 1)/7.$$

The cumulative dose (mg) of dacomitinib is the sum of the actual dose levels that the participant received (ie, total dose administered (mg)).

The dose intensity (DI) and the relative dose intensity (RDI) of dacitinib will be calculated for each participant during the study. The DI (mg/week) of dacitinib is defined as:

$$DI \text{ (mg/week)} = [\text{cumulative dose (mg)}]/[\text{treatment duration (weeks)}].$$

The RDI of dacitinib is defined as the ratio of the DI and planned dose intensity (d) and expressed in %.

$$RDI \text{ (%)} = 100 \times [DI \text{ (mg/week)}]/[7 \times d \text{ (mg/week)}].$$

6.5.3.2. Dose Reductions, Interruptions, and Delays

A dose reduction is defined as a non-zero dose that is less than the prior dose.

The number and percentage of participants with at least one dose reduction as well as a breakdown of dose reductions (1/2/3/ ≥ 4) will be summarized.

Reasons for dose reductions will also be summarized. Participants can contribute to more than one reason if multiple dose reductions occurred for different reasons, but will only be counted once per reason. Percentages will be calculated based on the total number of participants in Safety Set.

An interruption is defined as 0 mg dose administered on one or more days. (Note: A dose interruption is not considered a dose reduction). The number and percentage of participants with dose interruptions and the corresponding reasons will be summarized. Participants can contribute to more than one reason if multiple dose interruptions occurred for different reasons, but will only be counted once per reason. Percentages will be calculated based on the total number of participants in Safety Set.

The following defines how dose interruptions will be counted in the case of multiple dose interruptions:

- If an interruption occurs consecutively for at least two days due to the same reason, then it will be counted only once.
- If an interruption occurs consecutively for at least two days due to different reasons, then it will be counted for each reason
- If an interruption occurs for more than one day due to the same reason, but the days are not consecutive, ie. there is at least one dosing day in between, then each dose interruption will be counted as a different occurrence.

